### Follow-up Period

Visit Number	11	12	13	14	15	16
Week/Month (window)	Week 20 (±14 days)	Month 12 (±14 days)	Month 18 (±28 days)	Month 24 (±28 days)	Month 30 (±28 days)	Month 36 (±28 days)
Concomitant medications, treatments, procedures	X	X	X	X	X	X
Field assessment for SCC, BCC or neoplasia	X	X	X	X	X	X
Adverse events	X	X	X	X	X	X
AK count	X	X	X	X	X	X
Brief physical exam 		X	X	X	X	X

**Note: *Unscheduled/Early Termination***

*Upon completion of the last visit or during the study, an unscheduled visit may be required for any subject with a severe reaction, suspected pregnancy or an unresolved treatment-related AE or LSR, if deemed clinically significant by the investigator. Only assessments that require follow-up will be conducted if the subject is continuing in the trial. For early termination all trial assessments scheduled should be performed if possible.*

**10.7.2 Subject Eligibility**

Subject eligibility for the clinical trial will be checked according to the inclusion and exclusion criteria as specified in [10.4.1](#) and [10.4.2](#) at screening (Visit 1) and confirmed at Day 1 (Visit 2).

At Screening (Visit 1) subjects' demographic details (date of birth, sex, race, ethnic origin, height, weight, Fitzpatrick skin type) will be recorded. The subject will self-report their ethnicity (Hispanic or Latino, not Hispanic or Latino), and race (American Indian or Alaska Native; Asian, Black or African American; Native Hawaiian or Other Pacific Islander; White, Other). Relevant medical/surgical history, concurrent diagnosis, skin diseases and AK and SCC treatment history will also be recorded.

The subject's height will be measured without shoes and weight will be determined with indoor clothing and without shoes.

The abbreviated physical examination will include general appearance, regional lymph nodes and dermatologic examination of the skin in general.

Vital signs (resting blood pressure and heart rate) and oral or ear temperature will be recorded.

For female subjects of childbearing potential a urine pregnancy test will be performed at visits specified in [10.7.1](#).

Concomitant medication, treatments and procedures will be recorded at visits specified in [10.7.1](#).

---

Skin type of the subjects will be assessed by the investigator and recorded according to the following classification:

**Fitzpatrick Skin Types**

- I Always burns easily, never tans
- II Always burns easily, tans minimally
- III Burns moderately, tans gradually (light brown)
- IV Burns minimally, always tans well (moderate brown)
- V Rarely burns, tans very well (moderate brown)
- VI Never burns, deeply pigmented

Relevant medical history (including first date of AK diagnosis) and concomitant diagnoses will be recorded at the screening visit (Visit 1) and will be confirmed at Visit 2.

The selected treatment area will be identified by the dermatologist and documented on the study transparency using a three-point landmark technique. Detailed instructions for the three-point landmark technique are given in [Appendix IV](#). A biopsy will be taken of one AK lesion in the selected treatment area (see [10.7.4](#)) for histological confirmation of AK prior to randomisation at Day 1 (Visit 2).

**10.7.3 Clinical Assessment****10.7.3.1 Investigator Assessments**

Identification of the selected treatment area and dermatologic assessments of the selected treatment area must be performed by a dermatologist (board-certified or equivalent). The same dermatologist should attempt to perform all dermatologic examinations of each individual subject.

The (sub)investigator will make the following clinical assessments:

**Identification of the selected treatment area**

At Visit 1 identification of the selected treatment area should be documented on a study transparency using a three-point landmark technique (See [Appendix IV](#)). At all subsequent

---

visits, the transparency should be used to re-locate the selected treatment area for assessment of the treated skin on the face or scalp.

#### Clinical Assessment of Neoplasia in the selected treatment area

At all visits clinical assessment of the selected treatment area for neoplasia will be performed. If there is suspicion of SCC, BCC, or other neoplasia, a biopsy will be taken (see [10.7.4](#)).

#### Local Skin Responses

Assessment of local skin responses in the selected treatment area using the LSR Grading Scale should be performed at visit days as specified in the schedule of trial procedures ([10.7.1](#)).

Local skin responses are defined as erythema, flaking/scaling, crusting, swelling, vesiculation/pustulation, and erosion/ulceration. The presence/absence and grade of each LSR will be recorded using the LSR Grading Scale shown in [Appendix III](#). This grading scale will also be provided as hard copy to the site. Any local skin responses identified within the selected treatment area which do not match the criteria in the LSR Grading Scale should be reported as AEs.

#### AK lesion count

The number of clinically, visible AK lesions identified in the selected treatment area should be recorded at the visit days specified in the schedule of trial procedures (Section [10.7.1](#)). At Visit 1, the subject should have 5-9 clinically typical, visible and discrete AK lesions.

#### **10.7.3.2 Subject assessments**

Not Applicable

#### **10.7.4 Laboratory Assessments**

##### **10.7.4.1 Central Analysis**

##### Histological Assessments:

At Screening (Visit 1) a 3-4 mm punch biopsy will be taken from an AK in the selected area to confirm the diagnosis of AK as follows:

The biopsy area will be cleaned with an appropriate disinfectant. The skin will be numbed using an anaesthetic injection with a vasoconstrictor, e.g. adrenaline. Biopsies will be taken using a 3-4-mm disposable punch. If possible, the punch should contain tissue from the subcutis. The biopsy specimen will be removed from the punch very gently using forceps. Care should be taken not to squeeze the biopsy. The biopsy is transferred immediately into a plastic tube of approximately 10 mL containing 8 mL 10% neutral buffered formalin (formalin [40% formaldehyde] diluted 10 times in phosphate buffered saline, pH 7.4). It should be assured that the biopsy is submerged completely in the fixative. Specimens will be labelled with the study number (LP0041-63), subject (CRF) number and Visit. Haemostasis will be secured by pressure with gauze and stitching, if considered necessary. The (stitched) biopsy site will be left uncovered or sealed with Steristrip® as required.

The formalin fixed tissue will be shipped to the central pathology laboratory. The central laboratory's assessment determines whether the inclusion criterion of presence of AK in the biopsy is fulfilled.

Biopsies taken because of suspicion of SCC/BCC or other neoplasia will be processed as described above. The formalin fixed tissue will be shipped to a central pathology laboratory. The central laboratory will have a maximal turn-around time of 2 weeks to e-mail the evaluation back to the investigator for appropriate clinical action. Further details will be agreed with the central laboratory as to the number of pathologists to be involved in the final diagnosis of an SCC and the procedures to be employed to obtain agreement.

#### **10.7.4.2 Local Analysis**

A urine pregnancy test will be performed at the trial site at the visits specified in [10.7.1](#) in female subjects of child-bearing potential.

#### **10.7.5 Adverse Events**

*Any untoward medical occurrence in a patient or clinical investigation subject administered a pharmaceutical product and which does not necessarily have a causal relationship with this treatment. An adverse event (AE) can therefore be any unfavourable and unintended sign (including an abnormal laboratory finding), symptom, or disease temporally associated with the use of a medicinal (investigational) product, whether or not related to the medicinal (investigational) product. (ICH Harmonized Tripartite Guideline for Good Clinical Practice, E6 (R1)).*

---

A Serious Adverse Event (SAE) is any untoward medical occurrence that

- results in death
- is life-threatening
- requires inpatient hospitalisation or prolongation of existing hospitalisation
- results in persistent or significant disability/incapacity
- is a congenital anomaly/birth defect

or

- other medically important conditions\*), including SCC and BCC within the selected treatment area

\*) Events that may not be immediately life-threatening or result in death or hospitalisation but may jeopardise the subject or may require intervention to prevent one of the other outcomes listed in the definition above. Examples of such events are allergic bronchospasm, blood dyscrasias and convulsions.

Global Pharmacovigilance, LEO Pharma A/S is responsible for the assessment of headquarter expectedness according to LEO Pharma A/S procedures. The relevant reference document for this clinical trial is current version of the SmPC for ingenol mebutate gel (21) and subsequent updates as agreed between the head of Medical Department, and the medical director, Global Pharmacovigilance, LEO Pharma A/S. The current version of the SmPC for imiquimod (Aldara®) (appendix V) will be used for the assessment of expectedness for imiquimod.

At all visits, after Visit 1, the subject will be asked a non-leading question by the (sub)investigator: “How have you felt since I saw you last?” No specific symptoms will be asked for.

If there are no AEs to record (see [Table 2](#) and [Table 3](#) for reportable AEs), no further questions will be asked and “NO” should be stated. In case there are one or more AEs to record, “YES” should be stated and the investigator will record the event term, intensity, duration, suspected causal relationship to the investigational product and outcome.

It is important that the investigator also observes the subject for any changes not reported by the subject and records these changes where reportable (see [Table 2](#) and [Table 3](#)).

Only medically qualified personnel must assess AEs. A dermatologist (board-certified or equivalent) must do all dermatologic examinations, LSRs and AE evaluation in the selected treatment area.

If the informed consent is obtained before Visit 1, any medical changes until Visit 1 should be included in the medical history and not reported as an AE.

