### **Concomitant Medication, Treatments and Procedures from Week 20 in the Follow-up Period:**

In the Follow-up Period information will be collected regarding:

- concomitant medications, treatments and procedures used in the selected treatment area
- all use of ingenol mebutate or imiquimod whether inside or outside the selected treatment area
- medication or treatments which may suppress the immune system in the subjects

Procedures such as cryotherapy will be allowed in, and within 5 cm of the selected treatment area. Further, at the discretion of the Investigator and as according to nationally available product and treatment guidelines, the same treatment as originally administered is allowed (imiquimod or ingenol mebutate). Cross-over between imiquimod and ingenol mebutate is **not** allowed. Investigators will be encouraged to pursue these treatment options where clinically relevant and before employing other treatments.

Outside the selected treatment area (up to within 5 cm) all treatments will be allowed, although investigators will be encouraged to avoid cross-over between imiquimod and ingenol mebutate.

No other information on concomitant medications, treatments or procedures will be collected for subjects.

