#### 10.7.5.1 Reporting of Adverse Events

Events reported by the subject or observed by the (sub)investigator and that fall into any of the categories below must be recorded on the adverse event page of the CRF:

Table 2: Adverse Event Reporting for Visits until Week 20

Adverse Event	Inside treatment area	Outside treatment area including non-cutaneous events
BCC/SCC	All BCC/SCCs should be recorded in the CRF and reported to LEO as SAEs.	All serious and non-serious BCC/SCCs should be recorded in the CRF.  Serious BCC/SCCs should be reported to LEO as SAEs.
Other AEs	All AEs and SAEs should be recorded in the CRF.  Serious AEs should be reported to LEO as SAEs.	All AEs and SAEs should be recorded in the CRF.  Serious AEs should be reported to LEO as SAEs.

Table 3: Adverse Event Reporting for Visits after Week 20

Adverse Event	Inside treatment area	Outside treatment area including non-cutaneous events
BCC/SCC	All BCC/SCCs should be recorded in the CRF and reported to LEO as SAEs.	All serious and non-serious BCC/SCCs should be recorded in the CRF.  Only serious BCC/SCCs related to the treatment should be reported to LEO as SAEs.
Other AEs	All AEs and SAEs should be recorded in the CRF.  Serious AEs should be reported to LEO as SAEs.	Only SAEs related to the treatment should be recorded in the CRF.  These should be reported to LEO as SAEs.

*Please note: Local Skin Responses which match the criteria in the LSR Grading Scale are to be reported as LSRs in the CRF and not as AEs even if they require treatment. Any treatment should be recorded on the Concomitant medication page of the CRF together with the most important LSR (e.g. swelling should be reported as swelling-LSR).*

Adverse events should be described in the following manner:

The **nature** of the event will be described in precise English medical terminology (i.e. not necessarily the exact words used by the subject). Whenever possible, a specific diagnosis should be stated (e.g. allergic contact dermatitis).

For adverse events the anatomical **location** of the adverse event must be part of the adverse event description and may be described as the ‘in the selected treatment area’, ‘within 5 cm of the selected treatment area’, ‘more than 5 cm from the selected treatment area’ (with further specification for BCC/SCCs) or ‘not applicable’.

The **intensity** of the event will be described in terms of mild, moderate or severe according to the investigator’s clinical judgement.

- 

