Table 2-29 Adverse events from start of treatment to Week 20 by SOC and PT: safety analysis set

Table 2-30 Adverse events from Week 20 to end of trial by SOC and PT: safety analysis set

Table 2-31 Frequent adverse events ($\geq 5\%$ in any treatment group) from start of treatment to Week 20 by SOC and PT: safety analysis set

Table 2-32 Frequent adverse events ($\geq 5\%$ in any treatment group) from Week 20 to end of trial by SOC and PT: safety analysis set

Table 2-33 Adverse events from start of treatment to Week 20 by severity, SOC, and PT: safety analysis set

Table 2-34 Adverse events from Week 20 to end of trial by severity, SOC, and PT: safety analysis set

Table 2-35 Related adverse events from start of treatment to Week 20 by SOC and PT: safety analysis set

Table 2-36 Related adverse events from Week 20 to end of trial by SOC and PT: safety analysis set

Trial ID: LP0041-63	Date: 28-AUG-2019	Version: Final 1.0 Page 20 of 32
---------------------	--------------------------	-------------------------------------

Table 2-37 Related adverse events from start of treatment to Week 20 by severity, SOC, and PT: safety analysis set

Table 2-38 Related adverse events from Week 20 to end of trial by severity, SOC, and PT: safety analysis set

Table 2-39 Related adverse events by period, SOC, and PT: safety analysis set

Table 2-40 Adverse events from start of treatment to Week 20 by causal relationship, SOC, and PT: safety analysis set

Table 2-41 Adverse events from Week 20 to end of trial by causal relationship, SOC, and PT: safety analysis set

Table 2-42 Serious adverse events from start of treatment to Week 20 by SOC and PT: safety analysis set

Table 2-43 Serious adverse events by SOC and PT: safety analysis set

Table 2-44 Serious adverse events from start of treatment to Week 20 by causal relationship, SOC, and PT: safety analysis set

Table 2-45 Serious adverse events from Week 20 to end of trial by causal relationship, SOC, and PT: safety analysis set

Table 2-46 Skin malignancies inside treatment area by PT: safety analysis set

Table 2-47 Skin malignancies outside treatment area by PT: safety analysis set

Table 2-48 Adverse events leading to withdrawal from trial by SOC and PT: safety analysis set

Table 2-49 Adverse events from start of treatment to Week 20 by outcome: safety analysis set

Table 2-50 Adverse events from Week 20 to end of trial by outcome: safety analysis set

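### After Week 20, skin cancers outside the treatment area must all be recorded, but nothing prompts for one diagnosed or removed at another clinic between visits

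*Protocol*

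**What the plan says.** Protocol section 10.7.5 scripts the AE inquiry. At each visit after screening the subject is put one open, non-leading question about how they have felt since the previous visit. The section states "No specific symptoms will be asked for" and, where there is nothing to record, "no further questions will be asked". It then places a separate duty on the site: "It is important that the investigator also observes the subject for any changes not reported by the subject and records these changes where reportable".

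Section 10.7.5.1 applies to "Events reported by the subject or observed by the (sub)investigator". Its Table 3 governs visits after Week 20. Outside the treatment area, most AEs are recorded only if they are serious and treatment-related. BCC and SCC are the exception: "All serious and non-serious BCC/SCCs should be recorded in the CRF". Inside the area the rule is "All BCC/SCCs should be recorded in the CRF and reported to LEO as SAEs".

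Section 10.6.11 limits what is collected from Week 20 to three things: treatments and procedures in the selected area, any use of either study drug, and immunosuppressive treatment. It closes with "No other information on concomitant medications, treatments or procedures will be collected for subjects".

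The schedule in section 10.7.1 places a brief physical examination, which includes the skin generally, at Months 12, 18, 24, 30 and 36, but not at Week 20. SAP Appendix I lists Table 2-47, "Skin malignancies outside treatment area by PT: safety analysis set".

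**The concern.** Table 3 singles out BCC and SCC for complete recording outside the area, yet the protocol adds no step to elicit them. A painless lesion excised by another doctor months ago is not an obvious answer to a question about how one has felt. After Week 20 the procedure history will not reveal it either, because an excision outside the area is no longer collected. I found no directed question about skin cancers treated elsewhere and no instruction to check outside pathology records.

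What is at stake is the completeness of the outside-area skin malignancy table in a trial set up to study skin cancer risk. A reader of Table 2-47 would take it as a full count, because Table 3 of the protocol asks for one.

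**Working it through.** The plan gives no figure for this point. Its only sample-size figure, the precision statement in section 10.3, concerns the in-area endpoint. It reproduces as p + 1.96 × √(p(1 − p)/240), giving 2.26% at p = 1.0% and 4.48% at p = 2.5%. Nothing below depends on it.

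**Length of the unobserved intervals.** Inputs are the follow-up visits and windows in section 10.7.1 and the SAP's 30.4375 days per month, with Week 20 taken as day 140.

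- Week 20 to Month 12: 12 × 30.4375 − 140 = 225.25 days, and 225.25 / 30.4375 = 7.4 months. With ±14 days at each end: 6.5 to 8.3 months.
- Month 12 to 18: 6 × 30.4375 = 182.6 days = 6.0 months. With windows of ±14 and ±28 days: 4.6 to 7.4 months.
- Each of the three later intervals: 6.0 months. With ±28 days at each end: 4.2 to 7.8 months.

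The five intervals together span 36 − 140/30.4375 = 36 − 4.6 = 31.4 months of the 36.

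**Routes by which a cancer removed elsewhere after Week 20 could reach the CRF:**

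| Route | Outside the area | Inside the area |
|---|---|---|
| Open AE question (10.7.5) | Only if the subject mentions it | Only if the subject mentions it |
| Procedure history (10.6.11) | Not collected | Collected |
| Investigator observation (10.7.5) | Visible change or scar, no diagnosis | Same |
| Scheduled examination (10.7.1, 10.7.3.1) | General skin examination, Months 12 to 36 | Neoplasia assessment at every visit, with biopsy on suspicion |
| Central histology (10.7.4.1) | No outside-area biopsy scheduled | Biopsies taken on suspicion |

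Outside the area, a tumour still present at a visit can be found by examination. One that has already been removed leaves at most a scar, and a scar does not say whether it was a BCC, an SCC or something benign.

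**Size of the loss.** Let N be the number of outside-area cancers after Week 20, e the share removed elsewhere between visits, and v the share of those that come to light by report or by a scar that is followed up. The shortfall is N × e × (1 − v). The documents give none of the three, so no number can be put on it.

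**The case against.** The strongest reply is that the protocol does not rely on the subject alone. The rule bars prompting for symptoms. It does not bar every specific question, and closing the AE inquiry does not close the visit. The investigator must record unreported changes. The general skin examination falls at the end of all five intervals, so a fresh excision scar can be seen and asked about. A scripted non-leading question is also a deliberate choice that avoids inflating AE counts. All of this stands, and it is why the conclusion is under-recording rather than certain loss. It does not close the gap, because none of these routes requires anyone to obtain the diagnosis of a lesion that is gone.

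A reader might infer four stronger things that the documents do not support.

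- **Primary-endpoint events are being lost.** At the planning rates 240 × 1.0% = 2.4 and 240 × 2.5% = 6.0 events are expected per arm, so one lost event would be 1/6.0 = 17% to 1/2.4 = 42% of them. The arithmetic is right, but it would accompany any remark about a rare endpoint. In-area lesions have field assessment with biopsy at each visit and continued procedure collection, and SAP section 7.3.2 takes invasive SCC from biopsy.
- **Most SCCs depend on the open question.** In the pooled trials in section 8.2.1, 11 − 3 = 8 ingenol and 5 − 2 = 3 vehicle subjects had SCC only outside the area. That says where the tumours were. It does not say that they were removed elsewhere or went unmentioned.
- **A within-subject comparison of inside against outside is compromised.** Neither document plans one. The primary and secondary safety criteria are confined to the treatment field.
- **Open-label sites would probe more in one arm.** The scripted question is the same in both arms, and nothing in the documents indicates unequal probing.

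**Conclusion.** The point holds for cancers outside the treatment area that are treated at another clinic after Week 20. The protocol requires all of them, prompts for none of them, and no longer collects the procedure that would reveal them. Under-recording is likely across intervals of 6.0 to 7.4 months on the nominal schedule (4.2 to 8.3 months with visit windows). This rests on two judgements that the documents neither confirm nor refute: that some such cancers are treated elsewhere, and that some of these subjects will not mention them. The number missed cannot be computed.

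The consequence is confined mainly to SAP Table 2-47, a descriptive tabulation. The primary and secondary in-field results are not shown to be affected. This is a cheap improvement and does not threaten the trial's main conclusion.

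**What to change.** In section 10.7.5, keep the open question for all other AEs. Add one fixed question at each follow-up visit, worded identically in both arms: since the last visit, has any skin lesion been biopsied, removed or diagnosed as skin cancer, by anyone, anywhere on the body? If yes, record the date and the location category already defined in section 10.7.5.1 (in the area, within 5 cm, more than 5 cm away), and request the existing histology report.

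The cost is one question per visit and an occasional request for a report. The downside is that BCC and SCC become solicited events. The SAP already tabulates skin malignancies separately in Tables 2-46 and 2-47, so a note with those tables saying that they were solicited is enough.

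The protocol planned completion for Q2 2018 and the SAP is dated August 2019, so it may be too late to amend the procedure. If data collection has ended, state with Table 2-47 that outside-area skin cancers were not systematically solicited and that the counts may be incomplete.
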